## A. SPECIFIC AIMS

Obesity and sedentary lifestyle are associated with poor glucose control in persons with type 2 diabetes mellitus (T2DM) and resistance to behavioral interventions. While **diabetes self-management education and counseling (DEC)** has been improved and refined over the last 30 years, many persons with T2DM continue to have difficulty in achieving glycemic goals. Excessive daytime sleepiness, a frequent problem associated with obstructive sleep apnea (OSA), is a likely barrier to self-management of T2DM. The prevalence of OSA in persons with T2DM is notably greater than that for the general population, estimated to range from 40% to 97% depending on the degree of OSA severity and the age of the sample. In addition, results of previous studies suggest that OSA and T2DM not only co-exist but that sleep-related breathing disorders directly adversely affect glucose homeostasis. The most effective medical treatment for OSA is CPAP which eliminates apneas and hypopneas during sleep, and results in improved self-reported daytime functioning. Unfortunately, there is a notable gap in our understanding of the association between OSA and T2DM. The effect of CPAP treatment on glucose control remains unclear, with conflicting results possibly related to the previous studies having small sample sizes and not intervening in behavioral aspects of glycemic control. Therefore, the effect of OSA on behavioral aspects of diabetes self-management and the effect of CPAP treatment on diabetes education and counseling (DEC) remains unknown.

Data from our preliminary studies in persons with T2DM suggest that excessive daytime sleepiness may be a barrier to effective diabetes self-management and that poor sleep is associated with suboptimal diabetes self-management. We recently completed the *OSA, Sleepiness and Activity in Diabetes Management* study (OSA-DM) a double blind, randomized, placebo-controlled pilot study (R21 HL 089522, PI, [name]), that compared physical activity and glycemic control in adults with T2DM treated with active CPAP vs. those on sham-CPAP. Our preliminary data analysis suggests that CPAP treatment of OSA improves glycemic control and increases physical activity in persons with T2DM. Hence, we demonstrated the feasibility to recruit and retain subjects, a requirement for undertaking a larger study to test the efficacy of CPAP treatment in moderate-to-severe OSA in adults with T2DM.

The underlying premise of the proposed study from this new investigator is that OSA hinders diabetes self-management in adults with T2DM. The next step in understanding the effect of OSA on diabetes self-management is to determine the efficacy of CPAP treatment in improving diabetes outcomes in adults treated with CPAP compared to those on sham-CPAP. This proposal differs from the pilot/feasibility study in that we have a broader set of health outcomes that we are testing. We propose to enroll 210 adults with T2DM and moderate-to-severe OSA who have suboptimal diabetes self-management. We will conduct a 12-week double blind, randomized, placebo-controlled trial to determine if diabetes self-management outcomes and glycemic control are superior in subjects with OSA who are treated with CPAP and receive a DEC (**CPAP + DEC**) compared to control subjects (**sham-CPAP + DEC**). We will also explore the effect and robustness of treatment with CPAP (after 24-weeks) on glycemic control and factors associated with diabetes self-management.

**Aim 1 (Primary):** To determine if CPAP + DEC is superior to sham-CPAP + DEC for improving glycemic control. **H1:** Subjects who receive CPAP + DEC will have improved glycemic control compared to subjects with sham-CPAP + DEC at 6 weeks and 12 weeks.

**Aim 2 (Secondary):** To determine if CPAP + DEC is superior to sham-CPAP + DEC for improving diabetes self-management outcomes. **H2:** Subjects who receive CPAP + DEC will have better diabetes self-management outcomes (retention of information taught during the DEC classes, improved self-management behaviors, diabetes monitoring activities, increased physical activity, and decreased diabetes-related distress compared to subjects with sham-CPAP + DEC at 6 weeks and 12 weeks).

**Aim 3:** To explore adherence to CPAP (dose) and specific neuro-behavioral and physiological mechanisms (sleep quality, daytime sleepiness, mood, and vigilance that may mediate the effects of CPAP treatment on glycemic control and diabetes self-management outcomes (6 weeks and 12 weeks).

**Aim 4:** To explore the association between the durability of treatment of OSA (i.e. adherence to CPAP) and sleep quality, daytime sleepiness, mood, diabetes self-management, and glycemic control after 24 weeks of active CPAP in the full sample.

## B. PROTOCOL

**Design.** We will use a 2-group, randomized controlled design with treatment cross-over. Adults with T2DM who have an AHI  $\geq 10$  and suboptimal diabetes management, defined as an A1C  $\geq 6.5.0\%$ , will be randomized to one of two conditions: CPAP + DEC vs. control group - sham-CPAP + DEC (see Figure 2). We will compare the primary outcomes between the two groups on 1) glycemic control and 2) diabetes self-management outcomes. After cross-over, we will pool subject's 6 months data to evaluate robustness of treatment effects.

### Subjects and Recruitment

We will recruit adults with T2DM who are at high risk for OSA and suboptimal diabetes management from UPMC diabetes and sleep clinics in the Pittsburgh area (Monroeville, Mount Lebanon, and Mt. Nebo) in addition to the Oakland site, the community, and the Veterans Administration Pittsburgh Healthcare System (VAPHS).

At West Virginia University the

following methods will be utilized to identify potential subjects: EPIC electronic medical record review, work with primary care providers in the Family Medicine, Medical Group Practice, and Medical Specialties clinics. Brochures describing the trial will be made available in the outpatient settings.

University of Pittsburgh will enhance strategies that were successful in the pilot/feasibility study by using resources from the Clinical & Translational Science Institute (CTSI), which has developed community partnerships to assist in the recruitment of minorities. We will also recruit from completed studies and research registries by having letters sent to former participants in those studies. The PI/Project Manager and their staff of studies or research registries will identify the participants who may be appropriate to receive the letter and will send the letters. We will utilize social media advertisements developed by TrialSpark to recruit for the study. Potential participants are screened on-line after they have indicated their consent, they will receive follow-up email messages informing them if they are eligible. Those persons who are potentially eligible will receive telephone phone calls to confirm their eligibility and to set up an appointment for the first assessment. If individuals who receive the letter are interested in potentially participation in the DSTT study, they will be provided on the letter with DSTT contact information to obtain further study information. We will embed research staff in VAPHS and UPMC clinics to recruit subjects. We have initial contacts with the Hispanic Chamber of Commerce and the Latino Roundtable of Pittsburgh. We will directly recruit subjects by attending community events, speaking at public health events, placing flyers in the community, and through newspaper advertisements. We will expand recruitment by the co-investigators (Drs. [name], [name], and [name]) speaking to medical providers in internal medicine, geriatric medicine, public health, women's health, sleep, and diabetes clinics to discuss the study and encourage referral of potential subjects at the University of Pittsburgh and at the VAPHS. Drs. [name] and [name] at the VAPHS will assist in identifying potential patients. We will develop pocket guides on the purpose of the study and inclusion/ exclusion criteria for medical providers.

[figure not shown]
A brochure and flyer describing the study will be created for distribution; a "Dear Patient" letter will be generated for distribution to patients scheduled for diabetes and/or sleep clinic visits; a "Dear Colleague" letter will be generated and distributed to primary care, and women's health physicians in the community; newspaper advertisements describing the study and seeking individuals who snore will be circulated in the local newspapers. [name] will act as a consultant on recruitment.

### Eligibility criteria:-

When the potential subjects have met the initial eligibility criteria, and before the sleep study is conducted, their PCP will be contacted by the study coordinator to inform him/her of the potential subject's study participation and ask for their approval, if appropriate.

### The following criteria must be met for subjects to be randomized into the study:

- 1) T2DM with suboptimal glucose control (A1C  $\geq 6.5\%$ ),
- 2) AHI greater than  $\geq 10$  (ApneaLinkPlus®),

- 3) Age 18 years or older
- 4) Willing to be randomized to CPAP or sham-CPAP.

**Exclusion criteria include:**

- 1.) A1C > 11
- 2.) Gestational or type 1 DM
- 3.) Sleep duration < 4 hrs per day
- 4.) Change in diabetes medications during the previous 3 months
- 5.) Acute medical or surgical conditions or hospitalization  $\leq$  3 months (e.g. angina, stroke, major surgery, major depression or serious psychiatric conditions)
- 6.) Previous diagnosis of another sleep disorder, oxygen or bi-level PAP required
- 7.) O2 sat. < 75% for > 25% of the ApneaLinkPlus sleep study
- 8.) Cardiovascular events noted during overnight titration sleep study,
- 9.) Prior CPAP
- 10.) Persons in household with CPAP
- 11.) History of near-miss or auto accident during last 12 months
- 12.) Employed in safety sensitive job (i.e. truck driver or airline pilot)
- 13.) Non-ambulatory
- 14.) Regular use of hypnotic or alerting (e.g. modafinil) medications
- 15.) Excessive consumption of alcohol.  
Men: > 4 drinks a day and more than 14 drinks per week  
Women: > 3 drinks a day and > 7 drinks per week
- 16.) Claustrophobia to wearing mask
- 17.) Unable to speak, read & write English
- 18.) Pregnancy
19. Request of PCP

Exclusion criteria were determined to maintain subject safety and study integrity.

**Intervention and sham.**

Subjects in both arms of the study will be treated with the Respiromics System One Auto CPAP System. This system contains a wireless modem (Respiromics EncoreAnywhere™) that records adherence to CPAP nightly treatment and transmits the data to a password protected, web-based secure server. During the entire protocol, CPAP machines will be provided free of charge to the subjects; CPAP machines are being provided by the manufacturer (see Respiromics, Inc. Letter of Support). A standardized procedure to ensure adherence will be utilized in both treatment arms. The EncoreAnywhere™ system will record data for the entire time CPAP is in use. The Sleep Educator will upload participant adherence data from the EncoreAnywhere™ system on a regular (weekly) basis.

A sham circuit, a modification of the design of Farré and co-workers manufactured by Respiromics Inc., will create a CPAP placebo. This device was utilized by [name] (CATNAP study) and by [name] (APPLES study). This design places a hidden leak and a restrictor in the connector (Respiromics, Inc WhisperSwivel®) between the mask and CPAP tubing that allows air to escape and to prevent the rebreathing of carbon dioxide. The pressure will be set to 0.5-1 cm H2O at the mask to generate sufficient airflow to convince the CPAP naïve subject that they are receiving treatment, however; the pressure is insufficient to hold open the pharynx. The airflow generates a similar degree of blower noise from both circuits, providing CPAP naïve subjects with audible and tactile cues that do not differ between sham and active-CPAP and thus maintains blinding. The only difference between the two circuits is the mask pressure, which is the desired variable to be blinded. Data demonstrate that the sham-CPAP does not deliver therapeutic pressure nor produce clinically meaningful alterations in pre-treatment AHI, the nadir of oxygen desaturation, arousal index, and sleep efficiency. This design was used successfully by our research team in the pilot/feasibility study with subjects remaining blinded ( $p = .67$ ) to the group assignment.

Length of the intervention. The duration of the blinded intervention with sham comparison is 12 wks. This is based on previous studies in OSA patients demonstrating that improvements of objective sleepiness plateaus after 2 wks of treatment, results that are supported by several clinical trials that found significant improvement after 4 wks of CPAP treatment in subjective sleepiness, objective sleepiness, neuro-behavior outcomes, mood, and functional status. After the completion of the intervention, we will provide CPAP treatment to those subjects who were initially

randomized to sham-CPAP. We will follow all subjects for a total of 24 weeks of therapeutic CPAP treatment to evaluation durability of adherence to CPAP, glycemic control, and behavioral outcomes.

CPAP Titration Study/Sham-CPAP Titration. The nighttime CPAP titration PSG will be performed to determine the optimal level of CPAP needed to eliminate the subject's apnea. The CPAP titration PSG will be performed using standard techniques, with effective CPAP level defined as an AHI <5/hr with the minimum effective pressure for each subject. Patients randomized to the sham-CPAP arm will have titration studies that are performed identically to the CPAP titration except the standard CPAP connection will have a sham-CPAP restrictor piece added, the modified expiratory valve will be attached and pressure at the nose mask will be  $\leq 1$  cm H2O. The WhisperSwivel® connectors (sham and regular connectors) will be coded for the active CPAP intervention or the sham-CPAP group. A trained research Registered Polysomnographic Technologist at will choose the appropriate connector and record the number and the group (CPAP/sham-CPAP) in a secure file; this person is unblinded. The sham CPAP blower will be set at a pre-set level (this pressure is not transmitted to the subject, but determines the blower sound). The level of pressure for the blower of each sham CPAP participant will be displayed to participants as a "10 cm of H2O".

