Randomization. Subjects who meet all inclusion/exclusion criteria will be randomly assigned by computer program (R-track®) using a minimization algorithm with equal allocation to one of two treatment groups: 1) active CPAP set at a level of pressure that will abolish nocturnal respiratory disturbances, or 2) sham-CPAP (placebo) where the level of pressure will not abolish nocturnal respiratory disturbances. Use of a minimization algorithm will insure treatment balance on three factors: 1) the participant's baseline physical activity levels in terms of mean number of steps per day based on the SenseWear Armband® ( $< 5,000, \geq 5000$ ), 2) whether the subject had previous diabetes education, and 3) whether the subject is prescribed insulin. Minimization is a form of adaptive treatment allocation in which the probability of assignment to the treatment groups does not remain constant, but is determined by the current balance and/or composition of the groups. Treatment group assignment will be generated and stored in a secured database. Subjects and all research team personnel involved in further data collection will be blinded as to which group the subjects are assigned. The University of Pittsburgh site will randomize participants from all the recruitment sites (West Virginia University, VAPSHS, University of Pittsburgh).

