CPAP Titration Study/Sham-CPAP Titration. The nighttime CPAP titration PSG will be performed in to determine the optimal level of CPAP needed to eliminate the subject's apnea. The CPAP titration PSG will be performed using standard techniques, with effective CPAP level defined as an AHI  $<5/\text{hr}$  with the minimum effective pressure for each subject. Subjects randomized to the sham-CPAP arm will have titration studies that are performed identically to the CPAP titration except the standard CPAP hose will be replaced with the sham-CPAP hose, the modified expiratory valve will be attached and pressure at the nose mask will be  $\leq 1 \text{ cm H}_2\text{O}$ . The sham CPAP blower will be set at a pre-set level where pressure is not transmitted to the subject but produces the blower sound. Subjects will be loaned, without charge, either the CPAP or the sham-CPAP machines to take home for 12-wks. Subjects and their bed partners' will be instructed by the Sleep Educator on how to improve their sleep hygiene, OSA and CPAP therapy. Subjects will be encouraged to use CPAP/sham-CPAP every night; adherence will be monitored weekly with the EncoreAnywhere™ system.

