**Assessment 3 with Unblinding/ Debriefing.** (week 12- of CPAP/sham-CPAP use). Subjects will be sent the questionnaires, the SenseWear Armband® to use for 7-days before returning for Assessment #3. Subjects will return to the study site with those items, their glucose meter and pedometer. In addition, they will bring their CPAP/sham-CPAP machines and masks. Anthropometric measurements and a venipuncture to obtain fructosamine, A1C, and lipid profile will be done. Prior to being informed of his/her treatment condition, the subjects will be asked to which arm of the study they think they were assigned. The Project Manager/ Study Coordinator and/or PI will debrief the subject, answer any questions and provide a copy of their sleep and laboratory data.

Crossover to Active CPAP. The crossover to active CPAP is important because of two reasons: 1) ethical considerations and 2) the pilot/feasibility study subjects identified the possibility of eventually being able to try CPAP treatment was a major reason they considered participating in the study. VAPHS subjects who were in either the active and sham-CPAP group will be directed to the Sleep Center at the VAPHS for follow-up care. Non-VAPHS subjects in the sham-CPAP group will be offered the chance to have an actual CPAP titration study, as described above, receive the CPAP education and monitoring, and start CPAP.

**Assessment 4.** (week 24) All subjects are reassessed as described above; it is the final assessment for those who were initially on active CPAP. We will provide those subjects with a summary of their sleep and laboratory data. Those subjects that crossed-over to active CPAP will continue.

**Assessment 5.** (wk 36) Those subjects who crossed-over to active CPAP will have their final assessment (after 24 wks of active CPAP) performed as described above. Subject will receive a final debriefing by the Project Manager /Study Coordinator and/or the PI and a copy of their sleep and laboratory data.

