**Potential Challenges and Strategies.** We anticipate two potential problems: 1) management of a large-scale study and 2) loss of blinding by research staff involved in data collection. Our strategies are that [name] has the support of a cohesive team of co-investigators who are recognized in their areas of knowledge and have complementary expertise to this project. Our pilot/feasibility study demonstrated that study protocol successfully blinded subjects. We have developed a diagram of study personnel (see Appendix), duties, and blinding status to demonstrate how we plan to maintain blinding. We are aware that reducing subject burden is important. Although we did not have complaints of excessive burden in the pilot study and a 95% retention rate, we have further minimized burden with: 1) home testing of OSA with the ApneaLinkPlus® and 2) consolidating study activity to eliminate a separate discharge/exit evaluation. The two diabetes education sessions are part of standard diabetes care and the one-to-one format is more time efficient than regular group classes. The study sites (UPMC and VAPHS) are accessible by bus and we provide free parking to study participants. We will monitor seasonality as a potential confounder. We have the team and resources in place to implement this vitally significant study that will elucidate the role of sleep disorders as a previously unrecognized but significant barrier to the management of chronic disease.

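### All sham machines show one fixed pressure while active pressures are titrated individually, so the read-out can hint at the arm to staff who see or hear it, and the plan neither masks it nor checks staff blinding

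*Combined protocol and SAP*

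**What the plan says.** Section B, CPAP Titration Study/Sham-CPAP Titration (under Intervention and sham), sets the sham display: "The level of pressure for the blower of each sham CPAP participant will be displayed to participants as a" value of 10 cm H2O. The matching paragraph under Procedures adds: "The sham CPAP blower will be set at a pre-set level where pressure is not transmitted to the subject but produces the blower sound". For the active arm, the titration target is "effective CPAP level defined as an AHI <5/hr with the minimum effective pressure for each subject", and the Randomization paragraph also describes active CPAP as set at a pressure that abolishes the respiratory disturbances. Both arms use one device: "Subjects in both arms of the study will be treated with the Respiromics System One Auto CPAP System". The plan does not say what an active machine displays, and it describes no masking of the read-out in either arm.

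The blinding requirement, under Procedures, Randomization, is broad: "Subjects and all research team personnel involved in further data collection will be blinded as to which group the subjects are assigned". The titration technologist is identified as unblinded. Two kinds of later contact with the device or its user matter here:

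- The Sleep Educator instructs subjects on CPAP therapy and phones them at least weekly to raise adherence.
- Of the week-12 visit, the plan says: "In addition, they will bring their CPAP/sham-CPAP machines and masks". Each subject is told the arm at that visit by the Project Manager/Study Coordinator and/or PI, after giving an arm guess.

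Section C, Potential Challenges and Strategies, names "loss of blinding by research staff involved in data collection" as one of two anticipated problems. It refers to pilot evidence that subjects stayed blinded and to an appendix diagram of personnel, duties and blinding status.

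**The concern.** A constant on one side and a person-specific value on the other is a cue that anyone who knows the constant can read. The sham value is printed in the protocol, so staff who have read it need not work it out from debriefings. Because the value is shown to participants, it can also be mentioned on a telephone call.

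At stake is even delivery of care between the arms. Diabetes education is tailored to the individual, follow-up calls have a minimum number but no maximum, and the Sleep Educator intervenes to increase adherence. If staff lean towards one arm, effort and expectation can differ between arms, and part of an observed difference may come from coaching rather than from mask pressure. The Aim 2 questionnaires (DKT, SDSCA, PAID) are completed by the subjects who receive that coaching. The plan checks blinding only by the subject's guess, so a leak among staff would not be detected.

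**Working it through.** No figure in the plan bears on this point, so there is none to reproduce. The check applies Bayes' rule to the stated display and allocation.

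**Inputs**
- Allocation 1:1, planned 105 per group (Randomization; Sample Size Justification).
- Every sham machine shows 10 (CPAP Titration Study/Sham-CPAP Titration).
- Active pressure set "with the minimum effective pressure for each subject" (same paragraph); no values or spread given.
- q = share of active subjects whose machine also shows 10. Not in the documents; assumed 0.05 to 0.30.
- s = share of displays seen or heard by staff who know the sham value. Not in the documents; shown from 0 to 1.
- Active machines are assumed to show their set pressure. Not stated.

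**Formulas**
1. P(active | value other than 10) = 1, because no sham machine shows another value.
2. P(sham | value of 10) = 0.5 / (0.5 + 0.5q) = 1/(1 + q).
3. Correct guesses when every display is seen = 0.5 × 1 + 0.5 × (1 − q) = 1 − q/2.
4. Correct guesses when a share s is seen, the rest guessed at 50% = s(1 − q/2) + 0.5(1 − s) = 0.5 + s(1 − q)/2.

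**Results**

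| q | P(sham given 10) | Active subjects with another value: 105(1 − q) | Correct guesses, all displays seen |
|---|---|---|---|
| 0.05 | 1/1.05 = 0.95 | 99.75 | 97.5% |
| 0.10 | 1/1.10 = 0.91 | 94.5 | 95% |
| 0.20 | 1/1.20 = 0.83 | 84 | 90% |
| 0.30 | 1/1.30 = 0.77 | 73.5 | 85% |

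Dependence on s, for q = 0.30 and q = 0.05:
- s = 0: 50% and 50%, an intact blind.
- s = 0.25: 0.5 + 0.25 × 0.70/2 = 58.75%, and 0.5 + 0.25 × 0.95/2 = 61.9%.
- s = 0.5: 0.5 + 0.5 × 0.70/2 = 67.5%, and 0.5 + 0.5 × 0.95/2 = 73.75%.
- s = 1: 85% and 97.5%.

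The last column of the table is therefore an upper bound. How far practice falls below it depends on s, which the plan does not let one estimate.

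**The case against.** A reader might infer that the display identifies the arm to staff as soon as the first subjects have been debriefed. The documents do not support that, for these reasons:

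- What active machines show is not stated, and the sham display is described only as shown to participants. That blinded staff see it is an inference.
- A reading of 10 is not proof of sham, since an active subject may be titrated to 10.
- The Project Manager/Study Coordinator's instruction of subjects at Assessment 1 comes before randomization, when there is no arm to infer. Reports of falling asleep while driving come by telephone, and the response (unblinding and withdrawal) is the same for both arms.
- Machines are documented as brought in only at week 12, when that subject's blinded coaching is ending. The lists of what subjects bring to Assessment 2 and the description of the education sessions mention no machine. Adherence is followed by telephone and a web system.
- The plan calls for a standardized adherence procedure in both arms and for standardized education content.
- The appendix diagram covers blinding status and was not available for this review. It may separate the roles adequately.
- A1C and fructosamine are laboratory assays, steps are recorded by a device, and questionnaires are filled in at home. None is rated by staff.

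Most of this stands, and it limits the point to a possible leak of unknown extent. It does not remove the cue. The Sleep Educator's initial instruction and weekly calls remain plausible routes. Standardized content still leaves room for differences in effort. The pilot result (p = .67) concerns subjects, not staff, and a diagram of duties does not change what a machine shows.

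**Conclusion.** The point holds as an avoidable cue with no stated control and no staff check. If active machines display their set pressure, a value other than 10 reveals active treatment, and a value of 10 makes sham 0.95 to 0.77 likely for q of 5% to 30%. The 97.5% to 85% correct-guess rate is a ceiling for displays that are seen by someone who knows the sham value; with none seen, guessing stays at 50%. Both q and the share seen are assumptions.

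The consequence to guard against is performance bias in staff-delivered coaching and in the self-reported Aim 2 outcomes. The documents give no ground for claiming biased measurement of the A1C or fructosamine assays, or that staff blinding has in fact failed. The change is worth making because it is cheap. Its priority lies between worth considering and recommended, with medium confidence: the text on the sham display is clear, but actual staff exposure is not.

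**What to change.** 1. In both titration paragraphs (under Intervention and sham, and under Procedures), state what active machines display. Have the pressure read-out hidden or disabled identically in both arms where the device allows it, leaving mask pressure and sham settings as the protocol has them.
2. Where the device does not allow this, state who may see the display and keep education and data-collection staff from viewing it. Give the blinding status of the sleep educator, diabetes educator and assessor in the main text, consistent with the appendix diagram.
3. Add one form item recording the arm guess of the sleep educator, diabetes educator and assessor before each week-12 debrief, beside the subject guess already collected, and report the two together.

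Varying the displayed value among sham machines is less attractive. The blower level determines the sound, so this could alter a sham under which subject blinding held in the pilot, and mask pressure would have to be rechecked.

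The cost is a device-setting step and one form item, with no added subjects or visits.
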